InferiorGood-18-290

Behavioral Economic Methods for Assessing Tobacco Product Abuse Liability: Study 7

Study Protocol

3/16/2018

Protocol

Introduction

The 2014 Surgeon General's Report on the Health Consequences of Smoking concludes that changes in the physical design of cigarettes have caused an increased risk of developing lung cancer. One prominent cigarette design feature is filter ventilation, which has become increasingly common since the 1960s. Now, ventilated cigarettes now dominate the tobacco market. Filter ventilation alters cigarette burn rate and smoking topography. Ventilated cigarettes increase how much smoke is inhaled and therefore exposure to carcinogens. Moreover, because ventilated cigarettes most frequently feature low nicotine yield, smokers of highly ventilated cigarettes also smoke more cigarettes per day to compensate for reduced nicotine; this, in turn, further increases exposure to mutagens and carcinogens in tobacco smoke.

The Food and Drug Administration has the authority to ban filter ventilation. However, we currently don't know what such a ban would do to consumption of unventilated cigarettes--that is, whether smokers would switch to unventilated cigarettes and demonstrate similar levels of consumption, or whether smokers would reduce cigarette consumption or quit entirely. We also do not know if such a ban would result in the substitution of other nicotine products (e.g., electronic cigarettes, cigarillos, etc.). One way of understanding the effects of ventilation bans on tobacco consumption is to investigate unventilated cigarettes as an inferior good. An inferior good is an inferior substitute for a preferred product. This can be established by manipulating the account balance of a cigarette smoker. A good is determined inferior if its consumption decreases as the account balance for tobacco products increases. Thus, in the present studies, we will examine the behavioral economic demand for unventilated cigarettes in participants who normally smoke highly ventilated cigarette varieties (i.e., "ultra light" and "light" cigarettes). Using an account balance we provide, participants will purchase ventilated and/or unventilated cigarettes in three separate sessions across a range of prices (e.g., \$0.12, \$0.25, \$0.50, \$1.00, \$2.00 per cigarette). For some participants, some participants may also have access to alternative nicotine products such as cigarillos, gum, or lozenges. Participants will be asked to make these purchases under six different account balance conditions. From each session, purchases from one price will be randomly selected and participants will take home all cigarettes purchased at that price. Participants will later return to the lab to return any unused cigarettes and receive reimbursement for these unused products.

Participants

Up to 160 smokers will participate in this study. To participate, smokers must:

- 1) provide written informed consent,
- 2) be 18-65 years of age,
- 3) be an active smoker,

- 4) report smoking daily in the past month,
- 5) have stable self-reported mental and physical health,
- 6) be willing to try unventilated cigarettes or alternative nicotine products.
- 7) report that their usual brand of cigarettes features >~20% filter ventilation (i.e., "ultra light" and "light" varieties).

Individuals will be excluded from participating if they are trying or have immediate plans to quit smoking, are currently using prescription medication that might affect smoking or nicotine metabolism (e.g., varenicline, bupropion), have plans to move away from the area, or report regular use of electronic cigarettes, nicotine replacement therapy, or other alternative tobacco products (e.g., chewing tobacco). Females of childbearing age who report not having gone through menopause will be excluded from participating if they are pregnant (through urine screen at the time of consent) or lactating. Participants who meet DSM criteria for other substance dependence will be evaluated for eligibility on a case by case basis.

Recruitment

Participants will be recruited using a separate IRB protocol to screen cigarette smokers into a variety of smoking studies in our lab (see IRB #17-870), as well as study flyers.

To the extent possible, we will attempt to minimize obstacles to participation. For example, travel barriers may be addressed by providing transportation or parking costs for participants, and scheduling barriers will be minimized by offering a flexible study visit schedule.

Compensation may be provided for travel costs and time. We have a history of successful recruitment of cigarette smokers into research programs. All participants will enroll on a voluntary basis.

Consenting Process

Potential participants will be provided with the written consent form prior to visiting VTCRI or the Virginia Tech Corporate Research Center (VTCRC) (e.g., by email), if they wish. They will also be given additional time in a quiet room at VTCRI or VTCRC to read the form. VTCRI research staff will review each element of the written consent form with the potential participant. The potential participant will be given the opportunity to ask questions and will have as much time as they need to decide whether they would like to participate in the study. They will be encouraged to speak with whomever they wish before making this decision. Staff will reiterate that the potential participant can choose to decline participation in the study at that time or at any time thereafter without consequence. The potential participant and person obtaining consent will sign the consent form after the potential participant verbally states that s/he understands the conditions of the study, has no more questions, and chooses to participate.

Procedures

The study will take place over approximately four experimental sessions (one consent session, two purchase sessions, and one follow-up session) at the VTCRI's Addiction Recovery Research Center or the Virginia Tech Corporate Research Center. The initial consent session will last approximately two hours; the two purchase sessions and the final follow-up session in which subjects report consumption of, and/or return for reimbursement, their purchased cigarettes will last approximately 30 minutes to 1 hour each. Participants may also complete a brief (5-10 minutes) phone interview daily throughout participation, during which they will be asked to provide the number of study and non-study products they have used the previous day(s). They will be asked about their tobacco consumption at the laboratory sessions for days in which the data from the phone screen was not collected. Participants will also be asked to provide a breath sample for recent alcohol use at each session.

During the consent session, participants will provide informed consent (see section 4, above, for details), provide a baseline CO breath sample, and may also be asked to leave a urine sample. This sample may be tested for recent drug use and pregnancy, when applicable. During the consent sessions, and throughout the study, participants will also be asked to complete one or more of the following: the AUDIT questionnaire, questionnaires about cigarette use, craving withdrawal, delay-discounting tasks, cigarette demand, and ETM tasks.

Participants will then be given samples of the ETM cigarettes and/or alternative nicotine products (if that participant is assigned to ETM conditions that have more than cigarettes). Commercially available cigarettes will be used. Specifically, Marlboro Black 100's (~1.5% ventilation) and Marlboro Gold 100's (~28% ventilation). For participants that typically smoke menthol cigarettes, they will be given menthol versions of the Marlboro cigarettes. Importantly, the cigarettes will be labeled as "Cigarette A" or "Cigarette B." While both cigarettes are labeled with the Marlboro logo, they are not explicitly labeled as ventilated or unventilated. If participants are assigned to conditions where they will also purchase alternative nicotine products, they may be given samples of those products as well. Popular flavors of the alternative nicotine products will be made available. Participants will then take these samples home to use over approximately the next three days. The end of this sampling period will coincide with the first purchase session, at which time participants will return any unused samples.

Participants will then begin reporting to the laboratory approximately once every 2 days at a consistent time of day. Breath samples will be collected at each visit to measure CO. Participants will be informed that during the study they will be expected to only use products that we provide to them, but that the use of other products will not disqualify them from the study if they are accurately reported to us. This approach is intended to discourage the use of products that are not provided within the study while encouraging accurate self-reporting of such use. We will use a timeline follow-back procedure, or structured interview of recent product use to assess the use of other products outside of the laboratory.

At each of two purchase sessions, participants will “purchase” two days’ worth of either the Marlboro Blacks or Golds in one session. Here, they will report the number of cigarettes they would like to purchase across increasing prices (e.g., \$0.12, \$0.25, \$0.50, \$1.00, \$2.00 per cigarette). In one session, the price of both ventilated and unventilated cigarettes will increase in tandem across trials. In the other session, only the price of ventilated cigarettes will increase across trials. They will complete this task 6 times at each session. Once with the account balance that reflects what they typically spend on tobacco products (100%). The full range of account balances will be 140%, 120%, 100%, 80%, 60%, and 40%. At the end of each session, one price from one of the six times they complete the task will be drawn randomly and the participant will take home all cigarettes purchased at this price. Participants may also complete hypothetical purchase tasks. For some participants, alternative nicotine products such as cigarillos, gum, or lozenges may be available as well in both the real and hypothetical purchase tasks.

In each of the purchase sessions, participants will be able to purchase as many cigarettes (or alternative nicotine products) as their account balance allows, with the total price of the products purchased deducted from their account balance. Participants will be informed that the price of any unused products that are returned to the laboratory at their next visit will be refunded to their account. Thus, the number of cigarettes used outside of the laboratory will be calculated from the amount that is provided minus the amount that is returned. Before and after each session, participants may be asked to complete product evaluation surveys to measure changes over the course of the study. Participants will also be asked to return used cigarette filters (and cigarillo butts, depending on their availability) following each purchase session and the sampling period in order to qualify for the next session so that we may detect tampering or alteration of our method of ventilation blocking.

Participants will also complete a series of computerized and/or paper assessments (see attached task files for examples) during the consent session, purchase, and/or follow-up sessions. Likewise, in all sessions, participants may also be asked to leave a urine sample. This sample may be tested for recent drug use and pregnancy, when applicable.

To allow for payments that are both convenient and rapidly available, we may pay participants with reloadable prepaid cards through Greenphire ClinCard (www.greenphire.com), an FDIC-insured payment provider that specializes in clinical trial stipend payments that comply with IRB privacy regulations and considerations. At the beginning of the study, the participant will receive a prepaid MasterCard debit card that can be used anywhere that accepts MasterCard. As payments are earned in the course of the study, additional funds will be added to the account for that participant. Funds are immediately available when added and participants can check their balance as desired. This system will allow frequent, immediately available payments. Payments may also be made via check, however remote debit card payments and checks will be used most often.

Risks and Benefits

One risk of participation is embarrassment that may come from answering sensitive questions related to medical, psychiatric, and/or drug use history. Loss of confidentiality is another risk of participation. Additionally, because the present experiment allows and sometimes involves participants self-administering cigarettes or other alternative nicotine products, participants might experience adverse effects associated with the use of nicotine products (e.g., nausea, vomiting, dizziness, diarrhea, weakness, and rapid heartbeat) or withdrawal from nicotine (e.g., anxiety, irritability, difficulty concentrating). However, the amount of nicotine consumed is not expected to be different from what participants normally consume.

Data Protection

The linked code and identifying information document will be stored in a locked cabinet separate from the coded data, accessible only by members of the research team who have completed VT Human Subjects Training. The electronic version (REDCap) requires a VTC-issued user name and password and access is again limited to members of the research team who have completed VT Human Subjects Protection Training.

All data and participant binders will be stored in a safe place to protect confidential participant information. Safe places will include locked filing cabinets or locked rooms accessible only to study personnel. The full names of participants will not be listed on the outside of binders to protect confidentiality of study participants. Electronic data will be saved in secure, limited access shared drives on password-protected computers accessible only to the research team.

Access to study data will be limited to study personnel who have completed the Virginia Tech IRB Human Subjects Tutorial and who have been delegated the responsibilities of data collection, management, or analyses by the PI. Data collected from this study will be retained and destroyed in accordance with the center's policy that requires a 3-year retention period following final publication of the data.

Participant Compensation

Compensation for participation will be as follows:

\$20.00 for completion of informed consent

\$40.00 for completion of each purchase session (3 total in Study 1 and 2 total in Study 2)

\$40.00 for completion of the follow-up session

\$30.00 study completion bonus

Combined, the subjects could earn up to approximately \$210 in Study 1 and \$170 in Study 2 by completing all aspects of the experiment.

In addition, participants will receive approximately \$5 to \$40 each purchase session to purchase cigarettes. The amount each participant receives will be proportional to his/her real-world cigarette expenditure. In Study 2, it may also be smaller or larger depending on the account balance condition drawn. Account balances provided as part of the study to purchase study tobacco products will not be advertised as or considered compensation.

InferiorGood-18-290

Behavioral Economic Methods for Assessing Tobacco Product Abuse Liability; Study 7

Statistical Analyses Plan

3/16/2018

Statistical Analysis Plan

The consumption results of the assigned cigarette purchased in the Electronic Tobacco Marketplace will be analyzed using the demand function (Koffarnus, Franck, Stein, & Bickel, 2015):

$$Q = Q_0 * 10^{k(e^{-\alpha Q_0 C} - 1)}$$

Where Q is consumption of the commodity, C is the price, Q_0 is the derived initial consumption without cost constraints (demand intensity), k is the span of the function in logarithmic units, and α is the demand elasticity. Q and C are determined by the data and k is set to a constant determined empirically by the actual data, leaving only Q_0 and α as free parameters to be fitted. Analysis will proceed by fitting the above equation to individual participant data, then comparing demand intensity and elasticity across time (through sessions) and between groups using mixed-effects modeling. A random effect will be included to model repeated measures on participants, and socio-economic and other demographic variables will be statistically screened for inclusion using model-based hypothesis tests.

In order to measure the substitutability of the unassigned cigarette, the consumption results of the unassigned cigarette purchased in the Electronic Tobacco Marketplace will be analyzed using the substitution function (Hursh and Roma, 2008):

$$Q = Q_{alone} * 10^{I * e^{-\beta C}}$$

In this equation, Q_{alone} represents the maximum consumption of the fixed-price commodity (e.g., assigned cigarette) when the primary commodity has a price high enough to drive consumption to zero, β is the sensitivity of fixed-price commodity consumption to the price of the primary commodity, I is an interaction parameter that indicates whether the fixed-price

commodity is a substitute (positive β value), complement (negative β value), or independent (β value near zero) and Q and C represent consumption of the fixed-price commodity and cost of the primary commodity, respectively, and are known from date. This equation has three parameters (Q_{alone} , β , and β) that will be estimated from the experimental data using nonlinear regression. Analyses will proceed with the substitution equation being fit to individual subject data to generate subject-specific estimates of the maximum consumption, interaction, and sensitivity. These values will then be further analyzed to satisfy the goals of each experiment. Similar to the demand for the assigned cigarette, mixed model regression analyses will be used to include demographics and other covariates.

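### Q0 and alpha are fitted to purchases that the account balance caps, with no allowance for the cap, so both are biased by an amount that depends on the manipulated balance

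*SAP*

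**What the plan says.** The SAP fits a two-parameter exponentiated demand curve to each participant's purchases of the assigned cigarette. It explains that "Q_0 is the derived initial consumption without cost constraints (demand intensity"), reads alpha as elasticity, and fixes k at a constant whose value is not given. The only planned comparisons of Q0 and alpha are over sessions and between groups. There is no term for a spending limit, no censoring rule, and no mention of account balance as a factor.

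The protocol (Procedures) says that "participants will be able to purchase as many cigarettes (or alternative nicotine products) as their account balance allows". The task is repeated at six balances: "The full range of account balances will be 140%, 120%, 100%, 80%, 60%, and 40"%. The 100% level is described as "Once with the account balance that reflects what they typically spend on tobacco products (100"%). The prices are given as examples: "purchase across increasing prices (e.g., \$0.12, \$0.25, \$0.50, \$1.00, \$2.00 per cigarette". In one of the two sessions "the price of both ventilated and unventilated cigarettes will increase in tandem across trials", so both products draw on one balance. Under Participant Compensation, "participants will receive approximately \$5 to \$40 each purchase session to purchase cigarettes".

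The Introduction defines the target: "A good is determined inferior if its consumption decreases as the account balance for tobacco products increases".

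**The concern.** A purchase cannot exceed balance divided by price. Once that limit binds, the recorded number shows the size of the balance and no longer shows how much the person wanted. The lower the balance, the earlier along the price list this happens. A two-parameter curve fitted to the cut-off points becomes steeper, and its intercept moves away from what the person would take at no cost.

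The limit is also the experimental variable, so the error differs systematically between the six conditions. Q0 and alpha are the only demand measures that the SAP derives for the assigned cigarette, so an analyst asking about balance is likely to compare them. Part or all of any difference found could come from the cap. Averaging over balances does not cure this: in the example below all six fitted values of Q0 lie above the true one. The dollar balance is proportional to each person's real spending, so the bias also varies between participants.

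**Working it through.** The documents give no expected Q0 or alpha, so there is no planned figure to reproduce. The check takes fixed preferences, applies the cap, and refits.

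**From the documents:** prices $0.12, $0.25, $0.50, $1.00, $2.00 (examples); balances 40% to 140%; roughly $5 to $40 per session; the SAP demand equation.

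**Assumed:** two-day Q0 = 40, alpha = 0.002, k = 2, 100% balance = 40 × $0.30 = $12, one product (or the total of both), least squares on Q.

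**Step 1, wanted amounts.** Q = 40 × 10^(2(e^(−0.002×40×C) − 1)). At C = $0.12 the exponent term is e^(−0.0096) − 1 = −0.00955, so Q = 40 × 10^(−0.0191) = 38.3. The next two prices give 36.5 and 33.4. At $2.00, Q = 40 × 10^(2(e^(−0.16) − 1)) = 20.2.

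**Step 2, the cap.** At 40% the balance is 0.4 × 12 = $4.80. The affordable numbers are 4.80/0.12 = 40, 4.80/0.25 = 19.2, 4.80/0.50 = 9.6, 4.80/1 = 4.8 and 4.80/2 = 2.4. The cap binds at four of five prices. At 140% ($16.80) it binds only at $1.00 (16.8) and $2.00 (8.4).

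**Step 3, refit min(wanted, affordable) at each balance.** Without a cap the fit returns 40.0 and 0.0020. With the cap:

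| Balance | Bought at $0.12 | Bought at $2.00 | Fitted Q0 | Fitted alpha |
|---|---|---|---|---|
| 40% | 38.3 | 2.4 | 71.9 | 0.0174 |
| 60% | 38.3 | 3.6 | 53.3 | 0.0114 |
| 80% | 38.3 | 4.8 | 50.7 | 0.0082 |
| 100% | 38.3 | 6.0 | 47.8 | 0.0067 |
| 120% | 38.3 | 7.2 | 46.1 | 0.0055 |
| 140% | 38.3 | 8.4 | 45.4 | 0.0045 |

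With purchases in whole cigarettes, fitted Q0 is 74.2 at 40% and 45.7 at 140%. Fitted alpha is 0.0179 and 0.0047, a ratio of 3.8. Exactly 38 cigarettes are bought at $0.12 every time.

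**Step 4, other assumptions.**
- Balances of $10 to $16, k of 1.5 to 3, three alphas (27 cases): Q0 at 40% exceeds Q0 at 140% in all, by 9% to 85%. The ratio of alpha at 40% to alpha at 140% is 1.3 to 4.0.
- Balances of $5 to $40, Q0 of 20 to 40, alpha of 0.0005 to 0.008 (315 cases): Q0 falls throughout as the balance rises in 256, is flat in 15, ends lower but not steadily in 14, ends higher in 28, and is unchanged in 2. Where the lowest price is never capped (228 cases) it falls in 213, is flat in 15, and never rises.
- $5 balance, whole cigarettes, 40% to 140%: 30, 50, 65, 68, 58, 54. At $8: 55, 74, 57, 52, 51, 49. At $40: 46, 43, 41, 40, 40, 40.
- Log-scale fit at $12, whole cigarettes: 45 at 40% and 48 at 140%.
- With noise, Q0 at 140% is below Q0 at 40% in 64%, 90% and 81% of simulated participants at $8, $12 and $20.
- Two products sharing a balance: unventilated Q0 falls throughout in 50 to 66 of 84 cases, depending on how the balance is shared.

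**Step 5, raw purchases.** For one product or the total, min(wanted, balance/price) cannot fall as the balance rises. In the two-product runs, total unventilated purchases rose or stayed flat in all 84 cases under each sharing rule.

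**The case against.** A reader might infer that fitted Q0 always falls as the balance rises, and that the plan therefore manufactures an inferior-good finding. The documents do not support that, for three reasons. First, the direction depends on conditions: it needs a raw-scale fit and a lowest price that stays affordable, and the SAP does not state the error scale. Second, the Introduction defines inferiority by consumption, and a cap with fixed preferences does not make consumption fall. Third, the SAP never names balance as a factor, so it contains no test of Q0 against balance that could be wrong. The fall in alpha as the balance rises makes demand look less elastic, which does not by itself suggest inferiority. These objections stand, and they limit the point to one of bias and possible misreading.

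It can also be said that buying under a budget is ordinary demand, so the curves are valid given the balance. That does not rescue Q0. At a price near zero the cap no longer binds, so an intercept of 74 for someone who buys 38 at $0.12 is wrong on either reading.

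A last objection concerns the remedy: a joint censored fit could hide a real effect. If it forces one Q0 over all balances, it does. With a truly inferior good (Q0 falling from 40 to 20, $12 balance), such a fit returned a single Q0 of about 31. With Q0 free by balance and a common alpha, it recovered 39.5 falling to 19.9.

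**Conclusion.** The concern holds as a matter of confounding. Q0 and alpha, as the SAP would estimate them, mix preference with the account balance, and the balance is what the study manipulates. Alpha is inflated at low balances. Q0 is usually too high there (74 against 46, for a true 40, in the $12 example), is distorted in a different pattern near $5 to $8, and is little affected at $40 except at the lower balances. A difference in either parameter between balances is not evidence for or against an inferior good. Raw purchases, on which the protocol's own definition rests, do not show a false fall.

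The sizes rest on assumed Q0, alpha, k and dollar balance; the prices are only examples in the protocol. That the cap exists and that the SAP ignores it does not depend on those assumptions. This should be fixed before the analysis, but it does not invalidate the data, since the purchases needed for a sound test are recorded.

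**What to change.** Amend the SAP to:

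1. Test the inferior-good question on the number of each cigarette actually bought at a given price (for example the lowest) against account balance, and not on fitted Q0 or alpha.
2. Flag every purchase occasion where total spending comes within one cigarette's price of the balance.
3. Where Q0 and alpha are reported, fit flagged total purchases as right-censored at the affordable number. Let Q0 differ by balance; alpha may be shared over a participant's six curves. Do not impose a common Q0. In the two-product task a binding balance makes each amount an allocation choice, so censor the total and rely on item 1 for each product.
4. State that unadjusted Q0 or alpha is not evidence for or against an inferior good, and state the error scale of the fit.

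The cost is SAP wording and a modest change to the fitting code; balance, price and purchases arise from the task itself. The limit is identifiability. Fitted one curve at a time, a cap-aware fit returned Q0 = 40.0 wherever at least two prices were uncapped ($12 at 80% and above, $20 at 60% and above, $40 at all six balances). With one uncapped price it gave 40.9 to 47.7, and with none ($5 at 40% to 80%) Q0 could not be estimated. The number of such curves should be reported.

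### The SAP names no estimate or test of account balance, the factor by which the protocol defines an inferior good

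*SAP*

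**What the plan says.** Protocol, Introduction, gives the criterion: "A good is determined inferior if its consumption decreases as the account balance for tobacco products increases". It adds that manipulating the balance is the way to establish this, and that "Participants will be asked to make these purchases under six different account balance conditions".

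Protocol, Procedures, builds the factor into every purchase session: "They will complete this task 6 times at each session". The levels are given as percentages of usual tobacco spending: "The full range of account balances will be 140%, 120%, 100%, 80%, 60%, and 40" percent. The two purchase sessions differ in price regime. In one, both cigarette prices rise together; in the other, only the ventilated price rises.

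The SAP fits a demand function, with price as its only independent variable, to individual participants' data. It then plans on "comparing demand intensity and elasticity across time (through sessions) and between groups using mixed-effects modeling", with a participant random effect and screened demographic variables. It fits a substitution function, again in price alone, to the other cigarette. Those parameters go to unspecified further analysis serving each experiment's goals, with demographics and other covariates. Account balance appears nowhere in the SAP, and inferiority appears only in the study identifier.

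**The concern.** Balance is the manipulated factor, and the sign of its effect on unventilated purchases is the protocol's own criterion. An analyst could carry out every step of the SAP and still not say whether the criterion is met. Demand intensity, elasticity and the substitution parameters describe how purchases respond to price.

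If a balance analysis is added only after the data are seen, the price regime, the prices, the form of the balance effect and the direction counted as support would all be open to choice.

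**Working it through.** Neither document states a significance level, power, effect size or variance, so there is no planned figure to reproduce. The check is a count of the design, a comparison of texts, and one worked example.

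**1. Design.** Inputs from Procedures: 6 balances, 2 purchase sessions, 5 example prices ($0.12, $0.25, $0.50, $1.00, $2.00).
- Tasks per participant: 6 × 2 = 12.
- Purchase points: 6 × 5 = 30 per session, 60 in all, for each product.
- Range of balance: 140/40 = 3.5-fold.
- As a six-level factor, balance has 6 − 1 = 5 degrees of freedom.

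**2. Does any SAP term carry balance?**

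| SAP term | What it varies over | Carries balance? |
|---|---|---|
| Time (sessions) | Price regime; all six balances occur in each session | No |
| Groups | Not defined; the between-participant assignment visible in Procedures is access to alternative products ("if that participant is assigned to ETM conditions that have more than cigarettes") | No; balance varies within participant |
| Participant random effect | Participants | No |
| Screened variables | Socio-economic and demographic characteristics | No |
| Further analysis for the goals of each experiment; other covariates | Substitution parameters; content unstated | Permitted, not named |

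None of the 5 degrees of freedom for balance is used by a named comparison.

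**3. Pooled or separate fits?** The SAP does not say.
- *Pooled within a session:* the fit sees 30 price-quantity pairs. Reassigning the balance labels leaves those pairs unchanged, so the fitted parameters cannot reflect balance.
- *Separate:* there are 12 tasks to fit per participant, but no comparison of the resulting parameters by balance is named. At five prices each fit leaves 5 − 2 = 3 residual degrees of freedom for the demand function (two free parameters) and 5 − 3 = 2 for the substitution function (three).

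**4. Would a single linear balance slope be enough?** Not always. Hypothetical smoker (every value here is an assumption): usual balance $20, wants N = 40 cigarettes, prefers ventilated, and can buy unventilated at a fixed price f = $0.50. Let B be the balance in dollars and p the ventilated price. For p > f, unventilated purchases are u = B/f while B ≤ fN = $20. Above that, u = N − (B − fN)/(p − f).

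At p = $1.00:

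| Balance | 40% | 60% | 80% | 100% | 120% | 140% |
|---|---|---|---|---|---|---|
| B | $8 | $12 | $16 | $20 | $24 | $28 |
| u | 16 | 24 | 32 | 40 | 32 | 24 |

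- From 100% to 140%, purchases fall by 40 − 24 = 16, which is the inferior-good pattern.
- The linear slope over all six levels (mean 90, sum of squares 7,000) is 100 × (−800 − 720 − 320 + 400 + 960 + 1,200)/7,000 = 100 × 720/7,000 = +10.3 cigarettes per 100 points of balance.
- At p = $2.00, u = 16, 24, 32, 40, 37.3, 34.7 and the slope is +20.2.
- At the three lower prices ventilated costs no more than unventilated, so u = 0 and the slope is 0.
- Mean over five prices: (0 + 0 + 0 + 10.3 + 20.2)/5 = +6.1.

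With the same $20 balance, five other settings (f = $0.12 or $0.25 with 20 or 40 wanted; f = $0.50 with 20 wanted) give mean slopes between −5.7 and −15.5. The sign therefore depends on the fixed unventilated price, which the documents do not give, and on the quantity wanted.

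**The case against.** The strongest defence is that the SAP leaves room for balance. Its sentence on the goals of each experiment, its allowance for other covariates and its random effect for repeated measures could all accommodate it. Because each balance is a separate task over the full price list, one curve per task is also a natural reading. The Introduction states the aim broadly, as demand for unventilated cigarettes, and neither document designates a primary outcome, hypothesis or error rate.

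Much of this stands. The SAP does not exclude a balance analysis, and separate fits are at least as plausible as pooled ones. Permission is not specification, however: under either reading no balance term, contrast or direction is named.

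A reader might infer three stronger things that the documents do not support:
- *That the study cannot answer the question.* All six balances are to be collected within participant, so a balance term can simply be added.
- *That the planned fits will erase the balance effect.* This follows only if the tasks are pooled, which the SAP does not state.
- *That the plan carries a known inflated error rate.* If an analyst chose among 2 regimes × 5 example prices = 10 slopes at a two-sided 95% level, the chance of at least one false result in the inferior direction would be 2.5% with full correlation and at most 1 − 0.975^10 = 22.4% with independence. Both the family of ten and the level are assumptions, so these figures show analytic freedom and are not a property of this plan.

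**Conclusion.** The omission is real and should be corrected before the data are analysed. Followed exactly, the SAP does not determine whether unventilated cigarettes meet the protocol's definition of an inferior good. The number of named comparisons using balance is zero, across six levels and 12 tasks per participant. This conclusion rests on the text alone and needs none of the assumed values in the worked example.

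A reader might go on to infer that one linear balance slope, required to lie below zero, is the only correct remedy. The example shows otherwise: under assumed but coherent preferences, that rule would miss a fall in purchases that occurs once the balance covers the quantity wanted. What has to be settled in advance is a named contrast and direction; the particular contrast is for the investigators to justify.

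A secondary point is that the design covered by the SAP is unclear. The Introduction says "participants will purchase ventilated and/or unventilated cigarettes in three separate sessions across a range of prices", while Procedures lists "one consent session, two purchase sessions, and one follow-up session". Participant Compensation gives three purchase sessions for Study 1 and two for Study 2, and mentions a balance condition only for Study 2. The main finding does not depend on this.

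**What to change.** Add to the SAP:

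1. A mixed-effects model of unventilated cigarettes purchased, with account balance as a within-participant fixed effect, price, balance × price and participant random effects, estimated separately by price regime.
2. Before the data are seen, one primary regime, price set and balance contrast, and the direction that supports inferiority. The balance slope averaged over prices in the ventilated-price-only session is one option. Because purchases may rise and then fall, also fit balance as a six-level factor, or prespecify a contrast over balances at which the budget no longer limits the quantity bought.
3. The balance effect on ventilated cigarettes as a comparator.
4. A statement that the six balance tasks stay separate in any curve fits, and that by-balance fits are supportive, given 2 to 3 residual degrees of freedom at five prices.
5. Secondary: which of Study 1 and Study 2 the SAP covers, with the session counts in Introduction, Procedures and Participant Compensation reconciled.

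The cost is SAP wording and modest extra modelling on data the study already plans to collect. No visits or participants are added.
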